### 7.2.1 Day -1 Procedures

If the subject is on a bypassing agent prophylactic regimen, that regimen must be discontinued at least 24 hours prior to the administration of the first loading dose of Hemlibra (emicizumab). Bypassing agent prophylaxis must remain discontinued for the duration of the study.

### 7.2.2 Day 0 Procedures

#### 7.2.2.1 *Pre-treatment*

- Measurement of vital signs (blood pressure, pulse, temperature, and respiratory rate) and weight
- Confirmation of eligibility
  - Subject should not have received aPCC or rFVIIa within 24 hours prior to study drug administration
  - Subject should not have an active bleeding event

- Subject should not have any other temporary or permanent exclusionary event (at the discretion of the Study Investigator)
- Subjects who are receiving FVIII ITI therapy must discontinue ITI at this time and ITI must remain discontinued for the duration of the study
- Assessment of concomitant medication and supplements
- Assessment of adverse events
- Banked plasma sample [baseline antidrug antibody levels for Hemlibra (emicizumab)] for testing at the central laboratory
- Other diagnostic procedures as needed and ordered by the Study Investigator and recommended by the standard of care

#### *7.2.2.2 Drug administration*

- The loading dose for Hemlibra (emicizumab) is 3 mg/kg
- The vial(s) of Hemlibra (emicizumab) should be removed from the refrigerator and warmed to room temperature at least 15 minutes prior to administration
- Hemlibra (emicizumab) should be administered subcutaneously to the thigh, abdomen or upper arm

#### *7.2.2.3 Following drug administration*

- Observation at the IHTC for 30 minutes and assessment of adverse events
- For subjects with a history of hypersensitivity, the IHTC should follow up with the subject 24 hours after administration of Hemlibra (emicizumab) for assessment of adverse events

### 7.2.3 Day 7 Procedures

#### *7.2.3.1 Pre-treatment*

- Measurement of vital signs (blood pressure, pulse, temperature, and respiratory rate) and weight
- Assessment of concomitant medication and supplements
- Assessment of adverse events
- Subjects who are receiving FVIII prophylaxis must discontinue their FVIII prophylactic regimen at this time and FVIII prophylaxis must remain discontinued for the duration of the study

- Other diagnostic procedures as needed and ordered by the Study Investigator and recommended by the standard of care

#### *7.2.3.2 Drug administration*

- The loading dose for Hemlibra (emicizumab) is 3 mg/kg
- The vial(s) of Hemlibra (emicizumab) should be removed from the refrigerator and warmed to room temperature at least 15 minutes prior to administration
- Hemlibra (emicizumab) should be administered subcutaneously to the thigh, abdomen or upper arm at least 1-inch away from the previous site of administration

#### *7.2.3.3 Following drug administration*

- Observation at the IHTC for 30 minutes and assessment of adverse events
- For subjects with a history of hypersensitivity, the IHTC should follow up with the subject 24 hours after administration of Hemlibra (emicizumab) for assessment of adverse events

### 7.2.4 Day 14 Procedures

#### *7.2.4.1 Pre-treatment*

- Measurement of vital signs (blood pressure, pulse, temperature, and respiratory rate) and weight
- Assessment of concomitant medication and supplements
- Assessment of adverse events
- Other diagnostic procedures as needed and ordered by the Study Investigator and recommended by the standard of care

#### *7.2.4.2 Drug administration*

- The loading dose for Hemlibra (emicizumab) is 3 mg/kg
- The vial(s) of Hemlibra (emicizumab) should be removed from the refrigerator and warmed to room temperature at least 15 minutes prior to administration
- Hemlibra (emicizumab) should be administered subcutaneously to the thigh, abdomen or upper arm at least 1-inch away from the previous site of administration

#### 7.2.4.3 Following drug administration

- Observation at the IHTC for 30 minutes and assessment of adverse events
- For subjects with a history of hypersensitivity, the IHTC should follow up with the subject 24 hours after administration of Hemlibra (emicizumab) for assessment of adverse events

### 7.2.5 Day 21 Procedures

#### 7.2.5.1 Pre-treatment

- Measurement of vital signs (blood pressure, pulse, temperature, and respiratory rate) and weight
- Assessment of concomitant medication and supplements
- Assessment of adverse events
- Other diagnostic procedures as needed and ordered by the Study Investigator and recommended by the standard of care

#### 7.2.5.2 Drug administration

- The loading dose for Hemlibra (emicizumab) is 3 mg/kg
- The vial(s) of Hemlibra (emicizumab) should be removed from the refrigerator and warmed to room temperature at least 15 minutes prior to administration
- Hemlibra (emicizumab) should be administered subcutaneously to the thigh, abdomen or upper arm at least 1-inch away from the previous site of administration
- Assessment of adverse events

#### 7.2.5.3 Following drug administration

- Assessment of adverse events
- Banked plasma sample [antidrug antibody levels for Hemlibra (emicizumab)] for testing at the central laboratory
- Obtain data from an activity monitoring device (for the period from informed consent to Day 21) if standardly utilized by the patient and prior consent has been provided

## 7.3 Prophylactic Administration of Hemlibra (emicizumab)

Prophylactic administration of Hemlibra (emicizumab) will continue on a weekly basis (1.5 mg/kg subcutaneous dosing, or 3 mg/kg kg if dose escalation is determined appropriate by the

*Study Investigator [Section 5.3.3])* until subject withdrawal or study termination, whichever occurs first. The weekly injections will be administered by the subject, a trained caregiver, or a local healthcare provider, depending on the needs of the subject. Each subject will receive Hemlibra (emicizumab) for a minimum of 2 years and a maximum of 4 years based upon time of enrollment.

The subject will record the following in the patient diary at the time of each Hemlibra (emicizumab) infusion

- Adverse event assessment
- Any concomitant medication or supplement
- Date, time and quantity of Hemlibra (emicizumab) infused

#### **7.4. Subsequent Study Visits**

Subsequent study visits will be scheduled once a quarter, as is the standard of care for patients with hemophilic pseudotumor. These study visits will take place at the medical facilities of the subject's local physician, except for the annual and study close-out visits, which will take place at the IHTC. The first subsequent study visit will be 3 months ( $\pm 2$  weeks) following the first loading dose of Hemlibra (emicizumab).

The specific requirements of each visit are listed below. Depending on when a subject enrolls and when the study ends, the subject might not participate in all study visits beyond month 24. See **Appendix 2**.

##### **7.4.1 Study Visits at Months 3, 9, 15, 21, 27, 33, 39 and 45 ( $\pm 2$ Weeks)**

The subject will follow-up with their local physician at the intervals specified above.

During this visit:

- Measurement of vital signs (blood pressure, pulse, temperature, and respiratory rate) and weight
- Review of patient diary for completeness
- Patient study documentation will be submitted to the IHTC for review of compliance and data collection
- Review of AEs
- Review of concomitant medications and supplements
- Data will be obtained from an activity monitoring device if standardly utilized by the patient (if applicable)

#### 7.4.2 Study Visits at Months 6, 18, 30 and 42 ( $\pm 2$ Weeks)

The subject will follow-up with their local physician for a more detailed clinical review at the intervals specified above.

During this visit the following data will be collected and/or reviewed and transmitted to the IHTC:

- Measurement of vital signs (blood pressure, pulse, temperature, and respiratory rate) and weight
- CBC panel w/diff
- Review of breakthrough bleeding events requiring alternate hemostatic therapy
- Review of the number of hospital admissions
- Review of the development of anemia requiring transfusion or intervention
- Review of AEs
- Review of concomitant medications and supplements
- Review of patient diary for completeness
- Patient study documentation will be submitted to the IHTC for review of compliance and data collection
- Data will be obtained from an activity monitoring device if standardly utilized by the patient (if applicable)

#### 7.4.3 Annual Study Visits (Months 12, 24 and 36 $\pm 2$ Weeks)

The annual study visit will take place at the IHTC.

During this visit the following data will be collected and/or reviewed at the IHTC:

- Measurement of vital signs (blood pressure, pulse, temperature, and respiratory rate) and weight
- Radiologic evaluation (CT and/or MRI) to evaluate control of progression, stabilization or regression of pseudotumor
- Anti-drug antibodies (banked plasma sample)
- Repeated Haem-A-QoL and EQ-5D-5L
- CBC panel w/diff
- Review of breakthrough bleeding events requiring alternate hemostatic therapy
- Review of the number of hospital admissions
- Review of the development of anemia requiring transfusion or intervention
- Review of AEs
- Review of concomitant medications and supplements

- Patient diary will be collected for review
- Patient study documentation will be collected for review of compliance and data collection
- Data will be obtained from an activity monitoring device if standardly utilized by the patient (if applicable)

During this annual visit, a physical exam will be performed, used/empty vials of Hemlibra (emicizumab) will be collected, and a suitable quantity of Hemlibra (emicizumab) will be dispensed (see **Section 6.7**).

#### 7.4.4 Unscheduled Study Visits

Any unscheduled study visits with the subject's local hemophilia physician will be recorded in the CRF along with all relevant medical information (eg, reason for visit, diagnoses, scans, AEs, lab results, vital signs [blood pressure, pulse, temperature, and respiratory rate], weight, etc).

If a subject meets with a physician other than their local hemophilia physician, that information should be communicated to their hemophilia physician at the next scheduled quarterly study visit and appropriate medical information recorded in the CRF.

Hospitalizations should be recorded in the CRF along with relevant medical information (see **Section 6.11.3.2d**). These should be reported to the IHTC within 7 days of their occurrence.

AEs should be reported using the instructions in **Section 6.11.3**.

#### 7.4.5 Surgeries

All surgeries will be recorded in the CRF, which should minimally include the following information (see **Section 6.11.3** for additional reporting requirements):

- Procedure type
- Reason for procedure
- Planned or unplanned
- Date of procedure and length of hospitalization
- Hemostatic therapy provided pre-procedure (type, dose and dates)
- Hemostatic therapy provided post-procedure (type, dose and dates)
- Hemostatic outcome immediately post-procedure
- Hemostatic outcome at the end of hospitalization
- Adverse events experienced (including, but not limited to clots, thromboses and TMA)
- Vital signs (blood pressure, pulse, temperature, and respiratory rate) and weight

Hemostatic outcome for surgical treatment is defined using the standard ISTH rating scale shown below [Blanchette, Key et al. 2014].

Excellent	Intraoperative and postoperative blood loss similar (within 10%) to the non-hemophilic patient with no extra (unplanned) doses of FVIII/FIX/‘bypassing agents’ needed and blood component transfusions are similar to the non-hemophilic patient
Good	Intraoperative and/or postoperative blood loss slightly increased over expectation for the non-hemophilic patient (between 10 and 25% of expected), but the difference is judged by the involved surgeon/anesthetist/relevant healthcare professional to be clinically insignificant as evidenced by no extra (unplanned) doses of FVIII/FIX/‘bypassing agents’ needed and blood component transfusions are similar to the non-hemophilic patient
Fair	Intraoperative and/or postoperative blood loss increased over expectation (25–50%) for the non-hemophilic patient and additional treatment is needed such as extra (unplanned) doses of FVIII/FIX/‘bypassing agents’ or increased blood component use (within two-fold) of the anticipated transfusion requirement
Poor	Significant intraoperative and/or postoperative blood loss that is substantially increased over expectation (> 50%) for the non-hemophilic patient, requires intervention, and is not explained by a surgical/medical issue other than hemophilia, unexpected hypotension or unexpected transfer to an Intensive Care Unit due to bleeding or substantially increased blood component use (>2 fold) of the anticipated transfusion requirement

Medical details and outcome of all surgeries should be reported to the IHTC within 7 days of their occurrence.

## 7.5 Study Close-out Visit

All subjects will participate in a study close-out visit at the IHTC within 2 months of the planned study termination date.

During this close-out visit the following data will be collected and/or reviewed at the IHTC (depending on when the most recent annual visit took place and at the Study Investigator’s discretion, not all specified items may be necessary):

- Measurement of vital signs (blood pressure, pulse, temperature, and respiratory rate) and weight
- Radiologic evaluation (CT and/or MRI) to evaluate control of progression, stabilization or regression of pseudotumor
- Anti-drug antibodies (banked plasma sample)
- Repeated Haem-A-QoL and EQ-5D-5L
- CBC panel w/diff

- Review of breakthrough bleeding events requiring alternate hemostatic therapy
- Review of the number of hospital admissions
- Review of the development of anemia requiring transfusion or intervention
- Review of AEs
- Review of concomitant medications and supplements
- Review of patient diary
- Final Haem-A-QoL and EQ-5D-5L
- Patient study documentation will be collected for review of compliance and data collection
- Data will be obtained from an activity monitoring device if standardly utilized by the patient (if applicable)

Additionally, a physical exam will be performed and all used and unused vials of Hemlibra (emicizumab) will be returned to the IHTC.

Following the close-out visit, all subjects will be requested to meet with their local hemophilia physician to determine their ongoing treatment therapy/regimen.

## **7.6 End of Study/Early Termination Procedures**

The subject has the right to withdraw consent and exclude him/herself from the study at any time. The Study Investigator has the right to involuntarily withdraw a subject from the study at any time for any reason (eg, lack of compliance, unwillingness to complete study visits, SAEs, etc). The study may also be terminated early by Genentech as detailed in **Section 10.11**.

If the study is not terminated early, then the study will end 4 years following the date on the informed consent form of the first subject.

At subject withdrawal or study end/termination:

- All unused vials of Hemlibra (emicizumab) will be returned to the IHTC
- All empty vials of Hemlibra (emicizumab) will be returned to the IHTC
- The patient diary, study medical files and any activity data covering the final partial quarter of the study will be transmitted to the IHTC

Following subject withdrawal, the subject will be requested to meet with their local hemophilia physician to determine their ongoing treatment therapy/regimen.

## 8 QUALITY CONTROL AND ASSURANCE

This study will be sponsored by the IHTC. The IHTC research personnel undergo comprehensive clinical research training per Standard Operating Procedure (SOP) “Personnel Training, Competency and Qualifications” and comply with Food and Drug Administration (FDA), GCP and Institutional Review Board (IRB) regulations. All study staff will be CITI Trained

The Investigator will conduct the study in compliance with the protocol. Modifications to the protocol should not be made without agreement of the Investigator, the Sponsor, and Genentech. Changes to the protocol will require written IRB approval prior to implementation, except when the modification is needed to eliminate an immediate hazard(s) to subjects. The Sponsor will ensure the study is conducted in compliance with the protocol through various quality processes, including:

- Creating, implementing, and upholding SOPs for trial execution
- A quality scientific and medical design of the protocol
- Clinical investigator and site pre-assessment and selection
- Regulatory agency and ethics committee approval
- Developing and providing appropriate informed consent (language, transparency of benefits and risks) and obtaining IRB approval of the informed consent process
- Investigator meetings and training
- Adequate recording and reporting of data
- Periodic monitoring
- Audits

Regulatory authorities, the IRB, and/or the Sponsor’s clinical quality assurance group or designee may request access to all source documents, database, and any other applicable study documentation for an on-site audit or inspection. Direct access to these documents must be guaranteed by the Investigator, who must provide support at all times for these activities. All study sites may be audited by Genentech. Study sites will receive written notice in advance of any audit.

Additional standards and resources for Quality Assurance and Quality Control will be employed by the Sponsor during this study as appropriate.

## 9 PLANNED STATISTICAL METHODS

### 9.1 General Considerations

All data collected in this study will be documented using summary tables and subject data listings. Continuous variables will be summarized using descriptive statistics, specifically the sample size (n), mean, median, standard deviation, minimum and maximum. Categorical variables will be summarized by frequencies and percentages.

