### 4.2 Inclusion Criteria

Patients must meet the following criteria for study entry:

- Signed informed consent form from the subject, parent or guardian
- Diagnosis of congenital hemophilia A (baseline FVIII level <40%) with or without FVIII inhibitor, either high or low responding, regardless of titer
- Diagnosis of a hemophilic pseudotumor confirmed by radiologic assessment such as CT or MRI
- Any weight or BMI
- Medical documentation of prophylactic or episodic treatment (FVIII or bypassing agent) and the number of bleeding episodes for at least 16 weeks, and up to 6 months if available, prior to entry into the study
- Medical documentation of any need for PRBC transfusion or hospitalization for 6 months prior to entry into the study
- Subjects with a history of an inhibitor should provide documentation of the inhibitor history including date of initial diagnosis of inhibitor, peak titer, and agent utilized for hemostatic control
- Subjects with high titer inhibitors or those with low titer inhibitors who do not respond to FVIII must be willing to use rFVIIa as first line therapy for the treatment of breakthrough bleeding events
- Medical documentation of ITI therapy for subjects with a history of a FVIII inhibitor and ITI, including current FVIII inhibitor titer
- Willingness to discontinue any current prophylactic hemostatic regimen (FVIII or bypassing agent) and/or FVIII ITI therapy for the duration of the study
  - Subjects receiving FVIII prophylaxis must be willing to discontinue their FVIII prophylactic regimen immediately prior to their second loading dose of Hemlibra (emicizumab)
  - Subjects receiving bypassing agent prophylaxis must be willing to discontinue their prophylactic regimen at least 24 hours prior to their first loading dose of Hemlibra (emicizumab)

- Subjects receiving FVIII ITI therapy must be willing to discontinue ITI immediately prior to their first loading dose of Hemlibra (emicizumab)
- Willingness and ability to comply with scheduled visits, treatment plans, laboratory tests, and other study procedures, including the health-related questionnaires, activity tracking, and bleed diaries, using systems provided during the study

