## 6.10 Efficacy and Quality of Life Assessments

The primary outcome for this study is bleeding events specifically related to the pseudotumor over time; total bleeding events will also be recorded and analyzed.

All bleeding events will be recorded in the patient diary along with the following:

- The date and time of onset
- The anatomical location and severity
- The agent(s) used to control the bleed, the exact dose(s), the number of doses and the time(s) of administration
- The Study Investigator will determine whether the bleeding event was related to the pseudotumor based on a retrospective review of the clinical data

The efficacy of Hemlibra (emicizumab) will be determined by comparing the incidence of bleeding events and use of alternate hemostatic medication on study to the incidences prior to study enrollment and by changes over time.

The following should also be recorded and transmitted to the IHTC within 7 days of their occurrence:

- The admission of the subject to a hospital or medical facility (described in **Section 6.11.3**)
- Incidences of anemia that require transfusion or intervention
- All surgeries or deaths
- Any other AEs or SAEs noted and recorded by a physician

The efficacy of Hemlibra (emicizumab) will be determined by comparing the incidence of hospitalization and anemia that require transfusion or intervention on study to the incidences prior to study enrollment and by changes over time.

The following should be acquired during study visit 2 (if they were not performed within 1 month of study entry and if they are not considered suitable for study purposes) and at every annual study visit and the study close-out visit:

- Radiology (CT and/or MRI) to observe change in the size of the pseudotumor over time (ie, the progression, stabilization or regression of the pseudotumor)

The efficacy of Hemlibra (emicizumab) will be determined by the change in the size of the pseudotumor over time (ie, the control of progression, stabilization or regression of the pseudotumor).

The following will be used to determine changes in quality of life and activity level:

- Haem-A-QoL and EQ-5D-5L will be completed following screening and at every annual study visit and the study close-out visit

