## 7 STUDY ACTIVITIES

### 7.1 Study Visit 1: Informed Consent and Screening

- Informed consent signature and date
- Determination of eligibility
- Demographics (date of birth, race, gender, height)
- Weight
- Vital signs (blood pressure, pulse, temperature, and respiratory rate)
- Medical history review, including
  - Documentation of current or past infection of Hepatitis A, B and C
    - HAV:Ab
    - HBV:Ag and Ab (Core and Surface); if HBV:Ag positive, HBV viral load
    - HCV:Ab; if HCV:Ab positive, HCV viral load
  - Documentation of HIV infection (if Ab positive, viral load and CD4 count)
  - Review of at least 16 weeks, and up to 6 months if available, of data on prior use of hemostatic therapy and number of breakthrough bleeding events
  - Review of 6 months of data on prior need for hospitalization or for PRBC transfusion
  - Review of therapy prior to study entry with dose and interval and trough level if available on prophylaxis
  - Review of history of inhibitor including date of first positive test, highest documented titer and date
  - Review of concomitant medications and supplements
  - Date of development or identification of pseudotumor and documentation of radiologic (CT or MRI) scans
  - Review of surgeries and procedures
- Physical examination
- Lab screening (if adequate results are not available in the subject's medical records):
  - FVIII\*
  - aPTT
  - PT
  - VWF:Ag
  - FVIII inhibitor level (Bethesda assay)

---

\* If the subject has an inhibitor, then testing for FVIII level may not be medically necessary as FVIII is usually undetectable in such cases. Exceptions exist, such as for a patient who has mild hemophilia with an inhibitor that only recognizes infused FVIII and not endogenous FVIII.

- CBC w/diff
- CMP + direct bilirubin
- Serum pregnancy test for female subjects
- Lab screening for hepatitis (if adequate results are not available in the subject's medical records):
  - HAV:Ab
  - HBV:Ag and Ab (Core and Surface); If HBV:Ag positive, HBV viral load
  - HCV:Ab; If HCV:Ab positive, HCV viral load
- Lab screening for HIV (if adequate results are not available in the subject's medical files):
  - HIV:Ab; if HIV:Ab positive then HIV viral load and CD4 count
- Vaccinations: If the subject is not vaccinated, previously exposed, or immune to HAV and/or HBV then they will receive the first dose of the HAV and/or HBV vaccine. Subjects must follow up with their local provider to complete the recommended vaccination schedule\*

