### 9.5 Primary Endpoints

The primary endpoints are:

- The number of breakthrough bleeding events over time requiring the use of alternate hemostatic therapy (bleed rate) related to the pseudotumor
- The number of hospital admissions related to the pseudotumor
- The number of incidences of anemia requiring transfusion or intervention related to the pseudotumor
- The control of progression, stabilization or regression of the pseudotumor (ie, changes in size) as measured by yearly assessments including CT and/or MRI

The study investigator will determine whether the reported event was related to the pseudotumor based on a retrospective review of the medical data (eg, bleed location, patient symptoms, etc).

Efficacy analyses will be performed based on the parameters listed above. As there is no control group or placebo in the study, the on-study data will be compared to that listed in the subject's

medical files prior to study enrollment. The efficacy analyses will exclude data acquired during the 4 loading doses (study visit 2). Analyses will be performed on a per-subject basis and in aggregate. Sub-analyses will be considered based upon the included study population.

Demographic and baseline characteristics for all subjects will be summarized using descriptive statistics for continuous variables and frequencies and percentages for categorical variables.

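### Sections 9.1 and 9.5 give the before/on-study bleed comparison no effect measure, no interval, and no rule for observation windows that differ about 4- to 13-fold

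*Combined protocol and SAP*

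**What the plan says.** Section 6.10 names pseudotumor-related bleeding as the primary outcome and sets the test: "The efficacy of Hemlibra (emicizumab) will be determined by comparing the incidence of bleeding events and use of alternate hemostatic medication on study", against the incidence before enrollment and by changes over time. Hospitalization, anemia and pseudotumor size are also used to judge efficacy.

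Section 9.5 explains the comparator: "As there is no control group or placebo in the study, the on-study data will be compared to that listed in the subject's" medical files from before enrollment. Data from the loading period are excluded. On the level of analysis it says only: "Analyses will be performed on a per-subject basis and in aggregate". The summaries come from section 9.1: "Continuous variables will be summarized using descriptive statistics, specifically the sample size (n), mean, median, standard deviation, minimum and maximum". Section 9.1 also promises subject data listings.

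The two windows are set elsewhere. Section 4.2 requires documentation of "the number of bleeding episodes for at least 16 weeks, and up to 6 months if available, prior to entry into the study", and section 7.1 repeats that span for screening. For time on drug, section 7.3 states: "Each subject will receive Hemlibra (emicizumab) for a minimum of 2 years and a maximum of 4 years based upon time of enrollment". Section 7.4 adds that, depending on enrollment date, "the subject might not participate in all study visits beyond month 24".

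The endpoint is called a bleed rate, which implies dividing by time, but no formula or time unit is given. Section 9.2 sets about 10 subjects on feasibility grounds and expects that bleeds may be very few.

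**The concern.** A count from a few months is being compared with a count from several years in about 10 people. Annualizing puts both on one scale but does not make their distributions alike. One bleed in a 16-week look-back is already 3.25 per year, while one bleed in 204 weeks on study is about 0.25 per year. Medians and ranges can therefore differ between periods when nobody's bleeding has changed.

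The undefined aggregate adds a second problem. A mean of subject rates and a pooled rate can give different answers, and the choice could be made after the data are seen. With no interval, a reader cannot tell whether an apparent fall exceeds chance when the pre-study side may hold only a handful of bleeds.

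**Working it through.** The sample size has no statistical inputs, so there is no figure in the plan to reproduce.

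**Windows.** Look-back is 16 to 26 weeks (4.2, 7.1). Time on drug is 104 to 208 weeks (7.3), or about 100 to 204 after removing the loading period (9.5). The ratio runs from 104/26 = 4.0 to 208/16 = 13.0, or 100/26 = 3.8 to 204/16 = 12.8 after the exclusion. Early withdrawal would shorten the on-study side.

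**Why medians shift.** With a Poisson count at rate r per year over w weeks, the chance of no bleed is exp(-r·w/52). This exceeds one half when r < ln2·52/w, which is 2.25 per year at 16 weeks, 1.39 at 26 weeks, 0.36 at 100 weeks and 0.18 at 204 weeks. At r = 1, a subject has no bleed with probability 0.74 (16 weeks), 0.61 (26), 0.15 (100) and 0.02 (204).

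**Simulation with no true change.** Each of 40,000 trials had 10 subjects, look-back 16-26 weeks and on-study time 100-204 weeks, unrelated to bleed rate. Where two values appear in the median column, the first is for one common rate and the second for rates varying between subjects (gamma, dispersion 1). In the other columns a range spans the two models.

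| Assumed bleeds/yr | On-study median higher | Pooled ratio ≤ 0.70 | Pooled ratio ≥ 1/0.70 |
|---|---|---|---|
| 0.5 | 96% / 80% | 28% | 38-39% |
| 1 | 83% / 87% | 21-22% | 30% |
| 2 | 55% / 72% | 14-15% | 21-22% |
| 4 | 62% / 61% | 7-8% | 12-13% |

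Rises include trials with no pre-study bleeds. At 0.1 per year the medians tie in 92-95% of trials. At 12 per year the on-study median is higher in 55-56%, close to even. The mean of per-subject annualized rates is unbiased: 1.00 before and 1.00 on study at 1 per year.

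**When a pooled rate is biased.** It is biased if bleed rate is linked to window length. Take five subjects at 4/yr (26 weeks, then 100) and five at 1/yr (16 weeks, then 204), nobody changing.
- Pre-study: (10 + 1.54) bleeds / (5 × 42/52) years = 2.86 per year.
- On study: (38.46 + 19.62) / (5 × 304/52) = 1.99 per year. Ratio 0.70.
- Windows swapped between the groups: 2.14 before, 3.01 on study, ratio 1.41.
- Subject-stratified ratio, Σ O·b/(b+o) ÷ Σ B·o/(b+o), where B and O are bleeds before and on study, and b and o the weeks: 1.00.

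**What an interval would show.** Conditional on the total, the on-study count is binomial. The exact limits for p convert to a rate ratio by p/(1-p) × T_pre/T_on. At 1 per year the pre-study side averages only 10 × 21/52 ≈ 4 bleeds.
- 5 bleeds in 26-week look-backs versus 39 in 204 weeks: ratio 0.99, 95% CI 0.39 to 3.23.
- 3 bleeds in 16 weeks versus 19 in 100 weeks: 1.01, 0.30 to 5.35.
- An apparent halving, 8 bleeds in 4.02 person-years versus 29 in 29.2: 0.50, 0.22 to 1.26.

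**Changes over time.** If 10 subjects enroll evenly over 24 months, 10, 7, 5, 3 and 1 remain at months 24, 30, 36, 42 and 48. With constant rates of 1/yr in the first five and 3/yr in the last five, the aggregate runs 2.0, 2.0, 1.6 and 1.0 over years 1 to 4, although nobody changes.

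**The case against.** This is a single-arm study of a rare condition, sized on feasibility, with no hypothesis test. A descriptive plan is reasonable. Per-subject comparison and data listings are promised, so a reader of 10 rows need not depend on one median. That stands, and it is why the remedy is an estimate with an interval rather than a test or a power calculation.

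Two stronger readings are tempting and are not supported. A reader might infer that an unchanged rate will look worse on the median. That holds at assumed rates of about 0.5-1 per year, and up to 2 if rates vary between subjects. It does not hold generally, and the documents expect few bleeds without giving a rate. A reader might also infer that efficacy rests on pooled totals that flatter the drug by 30%. Section 9.5 defines no pooling rule, the mean of subject rates is an equally literal reading and is unbiased, and chance rises in the pooled rate are more frequent than chance falls. The 0.70 example needs heavy bleeders to have both the longest look-back and the shortest follow-up. The documents tie look-back to available records and follow-up to enrollment date, and nothing in them suggests that link.

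A conditional model also draws nothing from subjects with no bleeds in either period. At 1 per year this is about 4-24% of subjects, and at 0.1 per year 72-75%. That is a fair limit on the remedy and should be reported with it.

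**Conclusion.** The concern holds in a limited form. For a comparison that section 6.10 uses to determine efficacy, section 9 names no effect measure, no interval, no aggregation rule and no treatment of windows differing about 4- to 13-fold. At low assumed rates the named median usually points to worsening when nothing has changed (80-96% of trials at 0.5-1 per year). A pooled rate, if that is what aggregate means, is imprecise in both directions (falls of 30% or more in 21-28% of trials, mirror-image rises in 30-39%) and is biased only if bleed rate is linked to window length. All bleed rates, the Poisson model and the between-subject spread are assumptions. The missing interval and missing aggregation rule do not depend on them. The plan should be changed, but nothing here shows that it favors the drug.

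**What to change.** In section 9.5:

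1. Make the headline a within-subject on-study to pre-study bleed rate ratio that uses each subject's documented observation time (subject-stratified, or Poisson conditional on subject), with a 95% interval, exact or by subject-level bootstrap. Show each subject's counts, observation time and annualized rates beside it. State how many subjects had no bleeds in either period. Say what is reported if there are no pre-study bleeds at all, since the ratio is then undefined (probability about exp(-10 × 21/52 × 0.5) = 0.13 at a common 0.5 per year).
2. Define the aggregate analysis. Keep the section 9.1 summaries as description, but do not base the efficacy conclusion on medians or ranges compared across the unequal windows.
3. For changes over time, use months 0-24 for the whole group and only same-subject changes after month 24, when only earlier enrollees remain.

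The cost is a paragraph of plan wording and a few lines of code. Sections 6.2 and 6.10 already call for the bleed records. The interval will be wide and the efficacy claim more modest.
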